Date Revised:	January 19, 2017
Study Number:	HSM# 16-00041/ GCO#1: 16-0204(0001)

General exclusion criteria: Patient will not be enrolled in the study if ANY of the following criteria are present in the patient.

- Patients with ostial left main artery lesions or ostial right coronary artery lesions
- Female patients with child bearing potential not taking adequate contraceptives or currently breastfeeding
- Known allergy to acetylsalicylic acid or clopidogrel.
- Planned surgery within 12 months.
- History of bleeding diathesis
- Major surgery within 15 days
- Life expectancy < 12 months.
- Patients with kidney dysfunction (CrCl<30)

c) Number of Subjects

One hundred and fifty (150) consecutive patients with lesions requiring PCI of main vessel with drug eluting stent implantation for the treatment of stable CAD will be included in the study.

d) Study Timelines

This is a randomized study with one visit and no clinical follow-ups.

e) Study Endpoints

The primary endpoint is SB compromise defined as SB DS \geq 70%, or dissection or TIMI < 3.

The secondary endpoints

- SB FFR after main vessel stenting and its correlation with OCT imaging parameters before PCI
- OCT predictors of SB TIMI flow reduction after main vessel PCI
- Off-line analysis of SB stenosis by 3D-OCT and its correlation with FFR; correlation between 3D-QCA measurements, 3D-OCT, and FFR data.

Protocol Title:	Optical Coherence Tomography Predictors of Functionally Significant Side Branch Compromise after Provisional Main Vessel Stenting In Bifurcation Lesions Assessed by Fractional Flow Reserve (ORBID – FFR)
Principal Investigator Name/Contact Info:	[name]./ [name]/ [contact]
Primary Contact Name/Contact Info	[name] /[name] / [contact] [name] /[name] [contact]
Date Revised:	January 19, 2017
Study Number:	HSM# 16-00041/ GCO#1: 16-0204(0001)

- Association between calcification assessment by angiography and OCT imaging.
- FFR Device Success (ability to successfully deliver FFR wire to desired SB distal segment [n/150]).
- FFR Wire Workhorse Capability (proportion of patients [n/150] in which FFR wire able to serve as rail to deliver additional interventional devices to target SB lesion).

f) Procedures Involved in the Human Research

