Stable CAD patients with bifurcation lesions in whom provisional stenting strategy is planned, who have moderate or severe calcification in the main vessel lesion identified by angiography, SB stenosis 30-70% and SB reference diameter > 2mm will be enrolled in the study.

Moderate calcification will be defined as radiopaque density observed only during the cardiac cycle and typically involving only one side of the vascular wall, and severe calcification will be defined as radiopaque density noted without cardiac motion prior to contrast injection and involving both sides of the arterial wall. After completion of diagnostic angiogram and confirmation of subject eligibility, subjects will be randomly assigned to Rotational atherectomy (RA or Cutting Balloon Angioplasty (CBA)/PTCA group in a 1:1 fashion.

Patients in both groups will undergo PCI with stent implantation according to current standards of care. Lesion preparation including lesion pre-dilation, scoring or sculpting balloon angioplasty, and use of atherectomy and protection devices will be performed at the operator's discretion, followed by MV stenting. The operator will also decide in both groups about the length and size of the implanted stent. Procedural optimization, such as post-dilation or additional stent implantation will be performed based only on the angiographic findings, according to the discretion of the operator.

Protocol Title:	Optical Coherence Tomography Predictors of Functionally Significant Side Branch Compromise after Provisional Main Vessel Stenting In Bifurcation Lesions Assessed by Fractional Flow Reserve (ORBID – FFR)
Principal Investigator Name/Contact Info:	[name]./ [name]/ [contact]
Primary Contact Name/Contact Info	[name] /[name] / [contact] [name] /[name] [contact]
Date Revised:	January 19, 2017
Study Number:	HSM# 16-00041/ GCO#1: 16-0204(0001)

Optical coherence tomography (OCT) is an established medical imaging technique that uses light to capture micrometer-resolution, three-dimensional images from within optical scattering media will be performed to analyze plaque morphology, the extent and location of calcification, side branch size, angle, and ostial involvement.

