Patients in both groups will undergo (standard of care) a percutaneous coronary intervention (PCI), also known as coronary angioplasty, is a nonsurgical technique for treating obstructive coronary artery disease, including unstable angina, acute myocardial infarction (MI), and multivessel coronary artery disease (CAD) with stent implantation according to current standards of care. Lesion preparation including lesion pre-dilation, scoring or sculpting balloon angioplasty, and use of atherectomy (a minimally invasive endovascular surgery technique for removing atherosclerosis from blood vessels within the body.) and protection devices will be performed at the operator's discretion, followed by MV stenting.

The operator will also decide in both groups about the length and size of the implanted stent. Procedural optimization, such as post-dilation or additional stent implantation will be performed based only on the angiographic findings, according to the discretion of the operator.

The Pre and post stenting OCT + FFR for side branch are the research procedures.

OCT pullback will be performed after lesion preparation before stenting (OCT-PRE) and after PCI (OCT-POST). FFR measurement in the side branch will be performed, if the coronary angiogram shows SB DS < 70%, TIMI grade 3 flow and no dissection in the side branch.

To perform FFR measurements, the pressure wire will be passed through the struts of the MV stent into the SB and FFR will be measured at least 5 mm distal to the jailed SB stenosis. Adenosine will be infused through the

Protocol Title:	Optical Coherence Tomography Predictors of Functionally Significant Side Branch Compromise after Provisional Main Vessel Stenting In Bifurcation Lesions Assessed by Fractional Flow Reserve (ORBID – FFR)
Principal Investigator Name/Contact Info:	[name]./ [name]/ [contact]
Primary Contact Name/Contact Info	[name] /[name] / [contact] [name] /[name] [contact]
Date Revised:	January 19, 2017
Study Number:	HSM# 16-00041/ GCO#1: 16-0204(0001)

femoral vein at least 140 µg/kg per minute to induce maximal coronary blood flow.

g) Specimen Banking

Not Applicable

h) Data Management and Confidentiality

Confidentiality of subject medical information will be ensured by providing unique identifiers (Subject ID) for data transmitted from the enrolling centers to St. Jude Medical Center. Designated representatives will not receive identifiable subject information.

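### Both FFR-wire endpoints are fixed at n/150; Workhorse Capability then mixes rail performance with how often a side-branch device was used, and Device Success may be affected to a lesser degree

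*Combined protocol and SAP*

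**What the plan says.** Section 5(e), Study Endpoints, lists two secondary endpoints about the pressure wire, each with a fixed denominator of 150:

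- "FFR Wire Workhorse Capability (proportion of patients [n/150] in which FFR wire able to serve as rail to deliver additional interventional devices" to the target side-branch (SB) lesion.
- "FFR Device Success (ability to successfully deliver FFR wire to desired SB distal segment [n/150", the bracket closing there.

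Section 5(c), Number of Subjects, shows that 150 is total enrolment. It is not a count of wire or device attempts.

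Section 5(f), Procedures Involved in the Human Research, governs how often either step can occur:

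- No device in the side branch is required in every patient. Post-dilation is left to the operator's judgement, and "additional stent implantation will be performed based only on the angiographic findings, according to the discretion of the operator".
- FFR in the side branch is measured "if the coronary angiogram shows SB DS < 70%, TIMI grade 3 flow and no dissection in the side branch".
- The route of the wire is described for that measurement: "To perform FFR measurements, the pressure wire will be passed through the struts of the MV stent into the SB".

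The primary endpoint in Section 5(e) begins "The primary endpoint is SB compromise defined as SB DS" and covers stenosis of at least 70%, dissection, or flow below TIMI 3. The condition for measuring FFR is its exact complement.

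No section gives an attempt-based denominator or says how a patient without an attempt is counted.

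**The concern.** Both endpoints are named as properties of the wire: can it be delivered, and can it carry another device. A denominator of everyone enrolled answers a different question whenever some patients gave the wire no opportunity to succeed or fail.

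For Workhorse Capability the gap is built into the definition. The protocol offers no way to observe rail function except by taking a device over the wire, and that step is discretionary. A low value could mean a poor rail or simply that few side branches needed a device, and the reported figure would not show which.

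For Device Success the issue is conditional. Section 5(f) describes wiring for FFR only in uncompromised branches. Any compromised branch that is not wired stays in the 150 and cannot add to the numerator, so the rate would fall as the primary endpoint became more frequent, with no change in the wire.

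At stake is the interpretation of two descriptive results. Neither has a threshold, comparison or sample-size calculation attached.

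**Working it through.** **Where 150 comes from.** The sample-size text in Section 5 asks for 75 patients in each lipid group to detect an odds ratio of 2.8, and 2 × 75 = 150. With 25% read as the reference-group rate, the other group's rate is 2.8 × (0.25/0.75) / [1 + 2.8 × (0.25/0.75)] = 0.483. At 80% power and two-sided alpha 0.05 (alpha is assumed, as none is stated), the two-proportion formula with continuity correction returns 75 per group; without correction it returns 67. So 150 was sized for the lipid comparison and has no link to wire or device attempts.

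**Bounds that need no assumed rate.**

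- Workhorse on n/150 ≤ (patients with attempted device delivery over the wire) / 150.
- Device Success on n/150 ≤ (patients with attempted SB wire delivery) / 150.

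**Size for Workhorse.** Let d be the share of patients in whom device delivery over the wire is attempted and w the rail success per attempt. Then n/150 = w × d. The documents give neither; w = 0.95 is assumed and d is varied.

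| d | n/150 = 0.95 × d | Per attempt | Gap (points) |
|---|---|---|---|
| 20% | 19.0% | 95% | 76.0 |
| 50% | 47.5% | 95% | 47.5 |
| 80% | 76.0% | 95% | 19.0 |
| 100% | 95.0% | 95% | 0 |

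In whole patients at d = 20%, there are 30 attempts and 28 successes (28.5 rounded down). That is 28/150 = 18.7% (exact 95% CI 12.8 to 25.8) against 28/30 = 93.3% (77.9 to 99.2).

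**Size for Device Success.** Let t be wire delivery per attempt, c the compromise rate and f the share of compromised branches that are wired, with all uncompromised branches attempted. Then n/150 = t × [1 − c(1 − f)]. The values t = 0.98 and c = 0.20 (30 branches) are assumptions.

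| Compromised branches wired | Attempts | On n/150 (exact 95% CI) | Per attempt (exact 95% CI) |
|---|---|---|---|
| None (f = 0) | 120 | 118/150 = 78.7% (71.2 to 84.9) | 118/120 = 98.3% (94.1 to 99.8) |
| Half (f = 0.5) | 135 | 132/150 = 88.0% (81.7 to 92.7) | 132/135 = 97.8% (93.6 to 99.5) |
| All (f = 1) | 150 | 147/150 = 98.0% (94.3 to 99.6) | the same |

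**Can the reader recover the attempt count?** If no compromised branch is wired, yes, roughly: attempts are 150 minus the primary-endpoint count, here 150 − 30 = 120. If some are wired, no: in the half-wired row that subtraction would give 132/120 = 110%, which is impossible. The distortion is then smaller, but it cannot be corrected from the planned outputs.

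**The case against.** The strongest reply is that a whole-cohort denominator is a legitimate and conservative choice. Any such proportion is capped by the share with an opportunity to succeed, and an attempted-only rate can flatter the wire by leaving out the hardest branches. This stands as a reason to keep n/150. It does not make n/150 a measure of rail capability, which is what the endpoint's name promises.

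Several stronger readings are tempting, and the documents do not support them.

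- *The Workhorse distortion is always large.* That would follow if SB devices were used only in compromised branches. Section 5(f) does not confine them so; it leaves lesion preparation, protection devices and optimization to the operator. The gap shrinks to zero as device use approaches 100%.
- *Device Success is capped at one minus the compromise rate.* This holds only if no compromised branch is wired. The Workhorse endpoint itself foresees devices reaching the SB lesion over this wire, so some compromised branches may well be wired.
- *Patients without an attempt are counted as failures.* This is an inference from the fixed denominator. The text is silent.
- *The plan contradicts itself on when FFR is done.* Section 5(f) says "The Pre and post stenting OCT + FFR for side branch are the research procedures". Read as FFR both before and after stenting, it would give almost every patient an attempt. The sentences that follow define OCT before and after stenting, then describe FFR only through the stent struts. Section 5(e) likewise lists "SB FFR after main vessel stenting and its correlation with OCT imaging parameters before PCI". The natural reading is OCT at both times plus post-stent FFR: awkward wording and no separate defect.

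**Conclusion.** The point holds for Workhorse Capability on the definition alone: n/150 is bounded by how often a device was tried over the wire and so mixes wire performance with device use. Its size depends on a share the documents do not give, running from 76 points at 20% use to none at 100%, at an assumed 95% rail success.

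For Device Success the point is conditional. With 20% compromise and 98% delivery assumed, the formula gives a gap from none (all compromised branches wired) to 98.0 − 78.4 = 19.6 points (none wired). In the second case the attempt count is roughly recoverable, provided every eligible branch was attempted.

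It is worth correcting because the definitions as written can mislead and the repair is cheap. It does not touch the primary endpoint, the sample size or any test.

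**What to change.** - **Workhorse Capability:** report among patients in whom delivery of an additional device to the side branch over the FFR wire was attempted.
- **Device Success:** report among patients in whom delivery of the FFR wire to the side branch was attempted, stating whether attempts in branches that do not meet the FFR condition count.
- **Both:** give exact 95% confidence intervals. Keep n/150 alongside as a whole-cohort figure, with the number not attempted and the reason (SB compromise, no device used, other).
- **Data capture:** record attempt (yes/no) and reason for each endpoint in the eCRF. Section 5(h) says required data come through the eCRF but does not list its fields, so these may or may not already exist.
- **Wording:** clarify the sentence on pre- and post-stenting OCT and FFR in Section 5(f).

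The cost is the wording of two secondary endpoints and at most two pairs of eCRF fields, with no extra patients or procedures. There are two downsides. Intervals rest on fewer patients (30 instead of 150 in the 20% Workhorse example, 77.9 to 99.2). An attempted-only rate may also favour easier branches, which is why n/150 stays beside it.

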Intravascular imaging has provided new understanding of mechanisms associated with SB compromise following bifurcation PCI. Plaque shift has been traditionally considered as the principal mechanism for side-branch compromise after main vessel intervention. Rotational atherectomy(RA) has been advocated for the treatment of bifurcation lesions, since it can effectively remove plaque with minimal injury to adjacent normal arterial segments and potentially reduce plaque shifting, the “snow plow” effect. Intravascular ultrasound (IVUS) has been used for guidance in bifurcation lesions, aiding the visualization of plaque morphology at the main vessel and the side-branches and helping the selection of stent size and length as well as the selection of stenting strategy. However, due to the low spatial resolution of IVUS, all attempts for three-dimensional visualization have only focused on visualization of the luminal contour and not on the vessel morphology or the vessel-stent interaction. Optical coherence tomography (OCT) has ~10 times higher resolution than IVUS, which allows precise evaluation of the microstructure of the vessel wall including lipid pool, fibrous cap, calcification, and thrombus. OCT has been shown to constitute a valuable tool for PCI guidance and also the utility of three-dimensional (3D) renderings for

Protocol Title:	Optical Coherence Tomography Predictors of Functionally Significant Side Branch Compromise after Provisional Main Vessel Stenting In Bifurcation Lesions Assessed by Fractional Flow Reserve (ORBID – FFR)
Principal Investigator Name/Contact Info:	[name]./ [name]/ [contact]
Primary Contact Name/Contact Info	[name] /[name] / [contact] [name] /[name] [contact]
Date Revised:	January 19, 2017
Study Number:	HSM# 16-00041/ GCO#1: 16-0204(0001)

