 Mount Sinai	Protocol Title:	Optical Coherence Tomography Predictors of Functionally Significant Side Branch Compromise after Provisional Main Vessel Stenting In Bifurcation Lesions Assessed by Fractional Flow Reserve (ORBID – FFR)
	Principal Investigator Name/Contact Info:	[name]./ [name]/ [name]
	Primary Contact Name/Contact Info	[name] /[name] / [name] [name] /[name] [name]
	Date Revised:	January 19, 2017
	Study Number:	HSM# 16-00041/ GCO#1: 16-0204(0001)

Data analysis and Statistical methods:

T-test will be used. OCT off-line image analysis. For the accurate characterization of bifurcation lesions, OCT images will be analyzed systematically at 1 mm intervals according to previously validated criteria for plaque characterization using the St. Jude Medical Offline Review Workstation as we described previously. In addition, three-dimensional OCT software (QAngio OCT, Medis) will be used to obtain the information for the side branch ostium from a single main branch pullback as described recently in a validation of cut plane analysis (Figure 2). We will also perform three-dimensional quantitative coronary angiography (3D-QCA) using QAngio XA 3D software (Medis) to obtain the measurements of bifurcation angles, stenosis, and references. This software is dedicated to bifurcation lesions and has shown to provide highly accurate assessment of lesion dimensions and geometry based on 3D reconstruction of bifurcation lesions. Offline analysis of side branch for impingement of the ostium of SB leading to acute loss in SB diameter, area, carina shift and plaque shift will be performed and 3D-OCT parameters will be correlated with SB FFR measurements.

 Mount Sinai	Protocol Title:	Optical Coherence Tomography Predictors of Functionally Significant Side Branch Compromise after Provisional Main Vessel Stenting In Bifurcation Lesions Assessed by Fractional Flow Reserve (ORBID – FFR)
	Principal Investigator Name/Contact Info:	[name]./ [name]/ [contact]
	Primary Contact Name/Contact Info	[name] /[name] / [contact] [name] /[name] [contact]
	Date Revised:	January 19, 2017
	Study Number:	HSM# 16-00041/ GCO#1: 16-0204(0001)

[figure not shown]

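### Patients are randomised to RA or CBA/PTCA, but the procedures text leaves atherectomy in both groups to the operator; the OCT predictors labelled as preceding PCI are also measured after that step

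*Combined protocol and SAP*

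**What the plan says.** Section 5(f), Procedures Involved in the Human Research, states that after the diagnostic angiogram "subjects will be randomly assigned to Rotational atherectomy (RA or Cutting Balloon Angioplasty (CBA)/PTCA group in a 1:1 fashion". The following paragraph opens by referring to patients in both groups and covers lesion preparation: "use of atherectomy and protection devices will be performed at the operator's discretion". The same wording returns later in 5(f). No visible sentence requires RA in the RA arm, restricts it in the CBA/PTCA arm or defines crossover.

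On imaging times, 5(f) says "OCT pullback will be performed after lesion preparation before stenting (OCT-PRE) and after PCI (OCT-POST"). No earlier research pullback is described. Section 5(e), Study Endpoints, lists "SB FFR after main vessel stenting and its correlation with OCT imaging parameters before PCI" and "OCT predictors of SB TIMI flow reduction after main vessel PCI" as secondary endpoints. Section 1, Objectives, asks for OCT predictors of SB stenosis with FFR ≤ 0.8.

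On analysis, the statistical text says "T-test will be used" without naming the groups or the outcome. The sample size compares high and low lipid groups. No visible text uses the randomised arm as a comparison, stratum or covariate.

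**The concern.** There are two linked problems.

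1. **The allocation is not protected.** The modality that defines the arms is left to the operator in both arms. Discretion beyond the assigned device may be what was meant, but the text does not say so. Without a device rule and a record of the device used, readers of a randomised study cannot tell what each arm received.
2. **The predictors are measured downstream of the randomised step.** The Background says of RA that "it can effectively remove plaque with minimal injury to adjacent normal arterial segments and potentially reduce plaque shifting". On that rationale, arm could change what OCT-PRE shows and could also change the side branch. If arm affects both, and reaches the side branch by a route outside the imaged feature, a pooled predictor association partly reflects arm. A result from this pullback should not be presented as a finding from before PCI.

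**Working it through.** **Text side by side.** Sequence in 5(f): angiogram, randomisation, lesion preparation (atherectomy at discretion), OCT-PRE, stenting, OCT-POST, SB FFR if eligible. The 5(e) label for the SB FFR predictors places them before PCI. OCT-PRE is the only pre-stent pullback described, so the label and the sequence disagree.

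**The plan's own figure.** The plan gives 75 per lipid group for OR 2.8 at FFR-positive prevalence 25% and 80% power. Assume two-sided 5% and take 25% as the low-lipid rate. Then p2 = 0.25×2.8/(0.75+0.25×2.8) = 0.4828. The two-proportion formula gives 66.1 (67 per group), and with the continuity correction 74.4, so 75. The figure reproduces, but it is a lipid calculation and says nothing about arm.

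**Inputs for the size of possible confounding**
- From the plan: 150 patients, 1:1 allocation, FFR-positive 25% (or 20%).
- Assumed, because the documents give neither: an arm odds ratio for FFR-positive of 1.5, 2.0 or 2.8, and an OCT feature present in 60/40% or 70/30% of the two arms.
- Assumed: 120 patients with FFR as an alternative to 150, because "FFR measurement in the side branch will be performed, if the coronary angiogram shows SB DS < 70"%, with TIMI 3 flow and no dissection.

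**Null model.** Within each arm, feature and event are independent. Arm risks average 25% with the stated OR: 28.8% and 21.2% (OR 1.5), 31.4% and 18.6% (2.0), 34.3% and 15.7% (2.8). Collapse over arm.

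Example, arm OR 2.8 and split 70/30:
- Risk with the feature = 0.7×0.343 + 0.3×0.157 = 28.7%.
- Risk without it = 0.3×0.343 + 0.7×0.157 = 21.3%.
- Pooled OR = (0.287/0.713)/(0.213/0.787) = 1.49, where the within-arm OR is 1.
- Rejection by the pooled-variance two-proportion test, two-sided 5%, both tails: 18.2% with 75 per feature group, 15.5% with 60.

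| Arm OR | Split | Pooled OR | Rejection, n=150 | Rejection, n=120 |
|---|---|---|---|---|
| 1.5 | 60/40 | 1.08 | 5.5% | 5.4% |
| 1.5 | 70/30 | 1.18 | 7.1% | 6.7% |
| 2.0 | 60/40 | 1.15 | 6.5% | 6.2% |
| 2.0 | 70/30 | 1.31 | 11.1% | 9.9% |
| 2.8 | 60/40 | 1.22 | 8.2% | 7.5% |
| 2.8 | 70/30 | 1.49 | 18.2% | 15.5% |

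At 20% prevalence and arm OR 2.0 to 2.8, rejection is about 6–16% (150) and 6–14% (120).

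**Arm-stratified test.** A Cochran-Mantel-Haenszel test stratified by arm, without continuity correction (40,000 simulated trials per case, arm OR 2.0 and 2.8, 25% prevalence), rejects in 4.8–5.0% of null cases.

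**Price of stratifying when it is not needed.** True within-arm feature OR 2.8, no separate arm effect, overall risk 25%, 150 patients:

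| Feature split by arm | Power, pooled | Power, stratified |
|---|---|---|
| 50/50 | 75.6% | 75.1% |
| 60/40 | 75.9% | 73.5% |
| 70/30 | 75.7% | 67.8% |

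**The case against.** - **The only mechanism described is close to the no-bias case.** RA removes plaque, and OCT-PRE images plaque. If RA acts on the side branch only through the feature, pooling is unbiased and stratifying just costs power. No document describes a second route, or says that RA changes lipid classification, the predictor used for sample size. This stands, so a reader should not infer that the predictor results are confounded; the documents support only that they could be.
- **The aim is prediction.** An association pooled over preparation methods, measured just before stenting, is a legitimate quantity. This also stands. It argues for showing both estimates and correcting the label, not for discarding the pooled result.
- **The sizes are assumed.** The 18.2% needs the largest arm OR, numerically the same as the plan's lipid OR, together with the 70/30 split. At 60/40 the range with 150 patients is 5.5–8.2%. The model uses dichotomised FFR; nothing was computed for continuous FFR or TIMI flow.
- **The two parts pull against each other.** If operators choose freely, assigned arm predicts device weakly, and confounding would come from the device used, which an arm term does not remove. This is why the device rule comes first.
- **Figure 1 is not shown, and the t-test's groups are not stated.** Either could involve arm, and a device field may already be in the eCRF. The finding is therefore limited to visible text. It does not remove the need to correct a discretion clause that appears twice without exception.

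**Conclusion.** The point on the allocation holds from the text alone and needs no numerical assumption: as written, the operator may use or omit atherectomy in either arm. This should be fixed. The timing mismatch also holds, although 5(f) states the actual timing clearly and the correction is one of wording.

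Confounding by arm is a possibility. In the assumed cases it raises a nominal 5% test to between 5.5% and 18.2% with 150 patients. It is zero if arm affects neither or only one of feature and outcome, or acts only through the feature.

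Two stronger readings are tempting. A reader might infer that predictors of the primary SB compromise endpoint are biased, but the documents name OCT predictor analyses only for SB FFR (including FFR ≤ 0.8) and TIMI flow reduction; for SB compromise they ask for incidence. A reader might also infer that an RA versus CBA/PTCA comparison would be diluted by crossover, but no such comparison is named. The post-stent comparison of 3D-OCT and 3D-QCA with FFR is not affected by this point.

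**What to change.** **Main change, in section 5(f), both places.** State that the assigned device is used first; that operator discretion covers only preparation compatible with the assigned arm; that RA in the CBA/PTCA arm is bail-out only; and that departures in either arm are recorded as crossover. Tabulate device used by arm.

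**Secondary changes**
- In section 5(e), relabel the SB FFR predictors as measured after lesion preparation and before stenting.
- In the two named OCT-PRE predictor analyses, SB FFR (including FFR ≤ 0.8) and TIMI flow reduction, report an estimate stratified by or adjusted for randomised arm beside the pooled one.

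**Cost.** Less operator freedom, one eCRF field if the device is not already captured, and one stratum or model term. No new procedure or patients. The stratified estimate loses 0.5 points of power if the feature is balanced by arm, about 2 at 60/40 and about 8 at 70/30. It removes confounding by assigned arm only; the device rule limits operator-chosen departures, and the table shows those that remain.

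### The sample size needs an FFR result from all 150 enrolled patients, but the plan provides for side-branch FFR only where there is no angiographic compromise, makes no allowance for the loss, and does not label the measured subset

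*Combined protocol and SAP*

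**What the plan says.** Section 5 f (Procedures) provides for side-branch FFR "if the coronary angiogram shows SB DS < 70%, TIMI grade 3 flow and no dissection in the side branch". It also states: "The Pre and post stenting OCT + FFR for side branch are the research procedures". No other condition for measuring FFR after stenting appears in the text (Figure 1 is not shown).

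Section 5 e (Study Endpoints): "The primary endpoint is SB compromise defined as SB DS" of 70% or more, or dissection, or TIMI flow below 3. The secondary endpoints include "SB FFR after main vessel stenting and its correlation with OCT imaging parameters before PCI". Two wire endpoints carry the fixed denominator n/150: "FFR Device Success (ability to successfully deliver FFR wire to desired SB distal segment [n/150"]) and the proportion in which the "FFR wire able to serve as rail to deliver additional interventional devices to target SB lesion".

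The sample-size text under Data analysis and Statistical methods assumes FFR-positive prevalence of 20% or 25% and lipid groups of roughly equal size. It asks for at least 75 patients per group for an OR of 2.8. Its table gives 2.8 for 75 per group at 25% and 2.9 at 20%, both at 80% power.

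Section 5 c sets enrolment: "One hundred and fifty (150) consecutive patients with lesions requiring PCI of main vessel". Section 5 j says that subjects who discontinue are not replaced. Section 1 states the aim of estimating incidence and OCT predictors of FFR of 0.8 or below, without limiting it to a subset of branches.

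**The concern.** The condition for measuring FFR and the primary endpoint are mirror images. The trial exists to count side-branch compromise, so it expects some events, and each event is a branch with no planned FFR value. A branch that meets the condition can also go unmeasured if the wire cannot be delivered, and the plan foresees this by making delivery an endpoint. The sample size nevertheless treats every enrolled patient as contributing an FFR result.

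Two things are at stake. The stated 80% power depends on complete FFR data that the design does not provide for. And FFR incidence, odds ratios and correlations will come from a subset selected after stenting, while the aim reads as if it covered all branches. The n/150 denominators raise a smaller question of the same kind.

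**Working it through.** **1. Complement.** FFR is provided for if diameter stenosis is below 70%, and TIMI flow is 3, and there is no dissection. The primary endpoint is stenosis of 70% or more, or TIMI below 3, or dissection. Each clause negates its counterpart, so as worded no patient meets both.

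**2. Reproducing the plan's table.** Significance level, sidedness, formula and the meaning of prevalence are not stated. The best fit found is a two-sided 5% comparison of two proportions with continuity correction, taking the stated prevalence as the low-lipid rate p1. All four choices are inferred.

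For p1 = 0.25 and OR 2.8:
- p2 = OR·p1 / (1 − p1 + OR·p1) = 0.70 / 1.45 = 0.4828; difference d = 0.2328; mean m = 0.3664.
- Uncorrected n = [1.960·√(2m(1−m)) + 0.8416·√(p1(1−p1) + p2(1−p2))]² / d² = (1.3355 + 0.5565)² / 0.0542 = 66.07, or 67 per group.
- Corrected n = (66.07/4)·[1 + √(1 + 4/(66.07 × 0.2328))]² = 74.42, or 75 per group, as the plan states.

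Detectable OR at 50/75/100 per group:

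| Prevalence | Recomputed | Plan |
|---|---|---|
| 20% | 3.72 / 2.94 / 2.55 | 3.7 / 2.9 / 2.5 |
| 25% | 3.52 / 2.79 / 2.43 | 3.5 / 2.8 / 2.4 |

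Five cells agree after rounding; the sixth is 2.55 against 2.5. Alternatives fit less well. For the 25% row at OR 2.8, the uncorrected formula needs 67 per group. Reading prevalence as the overall rate needs 85 uncorrected or 95 corrected.

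**3. Reserve.** 2 × 75 = 150 results needed and 150 enrolled. With all 150 measured, power is 80.3%.

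**4. Unmeasured branches.** Let u be the share without an FFR value for any reason, equal in both lipid groups. The documents give no value for u, so 5–30% is an assumption. Results per group are n = 75(1 − u). Solve the correction formula backwards for the equivalent uncorrected n′; power is then Φ{[d√n′ − 1.960√(2m(1−m))] / √(p1(1−p1) + p2(1−p2))}.

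For u = 20%: n = 60, n′ = 51.72, and power = Φ[(1.674 − 1.3355)/0.6612] = Φ(0.51) = 69.6%.

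| Unmeasured (assumed) | FFR results | Power, OR 2.8, 25% row | Detectable OR, 25% row | Detectable OR, 20% row |
|---|---|---|---|---|
| 0% | 150 | 80.3% | 2.79 | 2.94 |
| 5% | 142.5 | 78.0% | 2.86 | 3.02 |
| 10% | 135 | 75.4% | 2.95 | 3.11 |
| 20% | 120 | 69.6% | 3.15 | 3.32 |
| 30% | 105 | 62.6% | 3.42 | 3.61 |

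**5. Sensitivity to the formula.** Without continuity correction, power for OR 2.8 in the 25% row is 84.8% with all 150 measured, and 82.9, 80.8, 76.0 and 70.2% at the same four values of u.

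**6. Incidence over all 150.** With k positive among n measured in total, incidence over all enrolled lies between k/150 and (k + 150 − n)/150. The width is (150 − n)/150 = u, so 10% unmeasured leaves a gap of 10 percentage points whatever k is.

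**The case against.** **The size of the loss is undocumented.** This stands. At 5% unmeasured, power falls by about two points, which matters little beside an uncertain prevalence. The mismatch is clear from the text; its importance depends on a rate that the sponsor must supply.

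**The formula is inferred.** This also stands. Without continuity correction, 10% unmeasured would still leave about 81% power. The plan's own table fits the corrected version better, so its stated figure has almost no reserve, but an exact count of patients who could be lost would be false precision.

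**The protocol says "if", not "only if".** FFR in a compromised branch is not forbidden, and a reader should not infer that it is. It is simply not provided for in the visible text. Offline 3D-QCA may also classify some branches differently from the procedural angiogram, so the complement is exact in wording and perhaps not in every analysed patient.

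**The n/150 denominators may be deliberate.** It is tempting to say that device success is capped below 100%. That would follow only if the wire is never passed in branches that fail the condition. Section 5 f describes wire passage for measurement ("To perform FFR measurements, the pressure wire will be passed through the struts of the MV stent into the SB"), while the rail endpoint suggests wider use. The text supports a request for clarification, not a finding of error.

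**Correlations with FFR necessarily use measured branches.** True, and that is a legitimate population. What is missing is the label.

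**Conclusion.** The point holds, as something the sponsor should fix. The design needs 75 + 75 FFR results from exactly 150 patients, while its own measurement condition and the possibility of failed delivery mean fewer are to be expected. With 10–20% unmeasured, power for OR 2.8 is about 75–70% and the detectable OR 2.95–3.15. This rests on the inferred formula, the 25% row, equal loss in both lipid groups and assumed rates.

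Three stronger readings are not supported:
- *The primary endpoint is compromised.* It does not use FFR and is unaffected.
- *The FFR results are biased in a known direction or by a known amount.* The documents do not settle this. The background's QCA figures (AUC 0.64, sensitivity 41.5%, specificity 83.1%) cannot fix the link between angiographic and FFR severity. In a bivariate-normal model, a correlation of about 0.3 matches the AUC but gives only about 33% sensitivity at that specificity.
- *The 25% can be used to forecast incidence bounds.* In the power calculation 25% is the low-lipid rate. At OR 2.8 the overall rate is (25.0 + 48.3)/2, about 36.6%, so using 25% as the overall rate would contradict the power figures.

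**What to change.** Leave the measurement rule as it is.

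1. Restate power and detectable OR for the expected number of FFR measurements. Give the assumed rate of unmeasured branches (angiographic compromise plus failed delivery), and state the significance level, sidedness, formula and meaning of prevalence.
2. Label FFR incidence, predictor and correlation results as applying to side branches without angiographic compromise in which FFR was obtained. Report the number unmeasured, by reason.
3. As a supplementary analysis, report incidence bounds over all 150, counting every branch without an FFR value, for whatever reason, first as negative and then as positive. Do not present the upper bound as the composite of FFR 0.80 or below or the primary endpoint: it also counts failed deliveries as positive, and procedural and offline stenosis readings may differ.
4. Reconcile the n/150 denominators in section 5 e with section 5 f by stating whether the FFR wire is passed in branches that fail the condition. If it is not, use attempted deliveries as the denominator.

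The cost is protocol wording and two simple bounds from data already collected, with no new patients or procedures. The downside is a less favourable stated detectable OR and incidence bounds that may be wide.
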